## **SPECIFIC AIMS**

The primary goal of this research project is to improve the health status and decrease hospitalization and death for patients discharged with heart failure (HF) via self-management education to patients, disease monitoring and medication titration through shared medical appointments (SMAs).

HF is a complex chronic illness where patients have a significant impairment of health status, with a high burden of morbidity and mortality. Half of Americans who develop HF die within 5 years of diagnosis and more than 1/3 of HF patients require frequent hospitalizations, or placement in long term care. Studies have found patient self-care behaviors in HF (e.g. medication/dietary noncompliance) and health system factors (e.g. care coordination, limited access, lack of education to patients and caregivers) played important roles in patient outcomes to the extent that 50% of the readmissions were judged to be possibly preventable.

Based on an operational model of effective chronic disease management (Chronic Care Model), one potential solution to addressing patient and system factors is redesign of care delivery, via SMA's, to provide self-management support to patients (and caregivers when available) while also performing disease monitoring and medication management in an environment of peer support. Our previous successes in conducting SMAs for diabetes suggested that these tasks can be accomplished in a coordinated and efficient manner by a multi-disciplinary team of non-physician health care professionals in an SMA setting to address patient and system factors related to low health status and outcomes surrounding patients with HF. However, there is a paucity of literature about HF-SMAs in general, and none in the effectiveness of HF-SMA in improving health status in HF. Given that patients discharged with HF are susceptible to declining health and hospitalization, it would be important to know if, how and to which groups, the successes in diabetes SMAs can be translated into HF, a disease with a higher morbidity and mortality. Although both Providence and Phoenix VAMCs have been conducting HF-SMAs for a combined total of 4 years, only 20-30% of eligible patients are referred to HF-SMA. A major barrier for implementation is the lack of effectiveness data. Thus, a rigorous assessment of HF-SMA effectiveness along with a pre-implementation assessment of potential barriers using a mixed method approach is needed prior to dissemination. This research, while focused at HF, will contribute to advancing implementation of SMAs as a team-based intervention for other chronic complex conditions.

We propose a 2-site randomized-controlled effectiveness trial with mixed methods to test a SMA intervention provided by a non-physician team of nurses, nutritionists, health psychologist, and nurse practitioners and/or clinical pharmacists, versus usual care to improve patient's health status and reduce hospitalizations and death in HF after discharge. In this trial, patients within 12 weeks of a HF hospitalization and/or IV diuretic therapy will be randomized to receive either HF-SMA versus usual care. The HF-SMA will consist of four sessions of 2-hour duration that occur every other week for 8 weeks or based on the clinics' appointment availability. The session will start with an assessment of patients and their needs followed by pre-assigned theme-based disease self-management education, followed by patient-initiated disease management discussion, and conclude with break-out sessions of individualized disease monitoring and medication case management. The study duration will be 180 days for all patients from the day of randomization. The specific aims are:

### **Primary Aim:**

Aim 1: To determine whether HF patients who participate in HF-SMA, as compared to usual care, experience better cardiac health status measured by Kansas City Cardiomyopathy Questionnaire (primary outcome), and overall health status (EQ-5D, secondary outcome), from baseline to 90 and 180 days.

*Hypothesis: HF patients who participate in HF-SMA will experience better cardiac and overall health status than patients who receive usual care from baseline to 90 and 180 days after randomization.*

### **Secondary Aims:**

Aim 2: To determine whether HF patients who participate in HF-SMA, as compared to patients who receive usual care, have fewer hospitalization or death, at 90 and 180 days

*Hypothesis: HF patients who participate in HF-SMA will have fewer hospitalizations or death than patients who receive usual care from baseline to 90 and 180 days after randomization.*

Aim 3: To determine whether HF patients in HF-SMA, as compared to patients in usual care, experience improvement in intermediate outcomes, namely, process (HF Self-Care behaviors) and physiologic (plasma BNP levels) measures from baseline to 90 and 180 days after randomization.

*Hypothesis: HF patients in HF-SMA, as compared to patients in usual care, will experience an increase in HF Self-Care behaviors and decrease in BNP levels from baseline to 90 and 180 days after randomization.*

**Aim 4:** To determine for HF-SMA, perceived benefits, areas in need of improvement, potential obstacles of implementation, and fidelity of the intervention across sites, by conducting (1) face-to-face interviews with a selected sample of patients and (2) telephone interviews with stakeholders (physicians of the patients who underwent HF-SMA and physician administrators).

## A. BACKGROUND & SIGNIFICANCE

The primary goal of this research project is to improve the health status and decrease hospitalization and death for patients discharged with heart failure (HF) via self-management education to patients, disease monitoring and medication titration through shared medical appointments (SMAs). Significance & Scope of the Problem

HF currently affects 5.1 million people in the US and 825,000 new HF cases are being diagnosed annually. HF is a leading cause of cardiovascular disease morbidity and mortality worldwide, costing 1-2% of the total healthcare budget in developed countries. In 2009 alone, 1 in 9 deaths in the US cited HF as a contributing cause. Half of Americans who develop HF die within 5 years of diagnosis and more than one third of HF patients require frequent hospitalizations, or placement in long term care. HF has a particularly higher impact among older people ( $\geq 65$  years old) and those with multiple co-existing illness, with  $\geq 90\%$  of HF-related deaths to occur among people  $\geq 65$  years. With 1 in 10 elderly living with HF and an aging population in the US, HF mortality and morbidity greatly impacts the health of our Veteran population. Indeed, our preliminary data from a random cohort of  $>100,000$  patients admitted with HF at VHA hospitals nationwide, showed the HF veteran population to be elderly (average age = 71 years), and has 30-day and one-year mortality rates of 6 and 30%, respectively, after their hospitalization. Since the main goal of the VHA is to improve health of the veterans, patient-reported health status is an important outcome metric for HF patients that includes symptom burden, functional status and health-related-quality-of-life, and an independent predictor of mortality, cardiovascular events, hospitalization and cost of care. HF patients have a significant impairment of health status, in both physical and mental health, in addition to declines in functional status.

### Patient and System Factors Related to Patient Outcomes in HF

Studies have found patient and health system factors played an important role in patient's health status and symptoms to the extent that 50% of the readmissions were judged to be possibly/probably preventable. Patient factors included behaviors such as medication (15%) or dietary sodium (18%) non-compliance, and failure to promptly seek medical attention (20%), and social factors such lack of a social or peer support to call for problems. Behavioral factors were a key component and calls for the need of a structured learning and behavioral modification approach such as the SMA approach. Factors contributing to medication non-adherence included too many medications, dissatisfaction with medicine information provided, and concerns about the potential adverse effects of medicines. Barriers related to dietary sodium restrictions include low knowledge about dietary sodium, and the poor taste of food on the low sodium diet. Lack of knowledge in early symptoms of HF decompensation was one of the main reasons for treatment-seeking delays, with a median duration of early symptoms to treatment of 5-7 day delay. Hospital factors included inadequate care coordination (discharge planning and/or follow-up), inadequate patient and caregiver education and support (e.g. who to call for problems), and limited access to providers after hospitalization. Traditional settings of one-to-one visits are labor intensive and inefficient in addressing these multi-disciplinary needs. SMAs, described further below, is poised to fulfill the above needs by providing education and behavioral intervention, medication management and disease monitoring in a group setting of peer support.

### SMA for Chronic Disease Management in HF and Gaps in the Evidence

Based on an operational model of effective chronic disease management (Chronic Care Model), one potential solution to addressing both patient and health system factors is redesign of care delivery, via "SMA's" to educate patients (and caregivers if available) about HF self-care thereby enabling behavioral modification while also performing disease state monitoring and medication management. **Group medical visits or SMAs** are defined as visits in which several patients meet with one or more provider(s) at the same time, and typically involve a multidisciplinary team of a health psychologist, a prescribing provider, and a documenter. An important distinction is that SMAs are not 'classes' because they provide individualized medication prescribing and clinical monitoring of patient health status. SMA also distinguishes itself from the traditional case management or disease management models, which is usually provided by one provider to one patient at a time. As such, SMA is a comprehensive disease management program, where several patients with the same disease can meet with multidisciplinary health professionals in the same setting, in a coordinated fashion, for efficiency and improved access, and where behavioral change can be facilitated through education and group peer support (details below under behavioral change). Thus, we postulate that the change in self-care behaviors, and individualized medication prescribing and clinical monitoring in HF-SMA will lead to improvement of patient's health status, decrease in symptoms and BNP levels (a biological measure of the severity of HF) and subsequent decrease in hospitalizations and possibly mortality for HF.

Although studies have shown that some disease management programs may improve patient outcomes in HF, the effect and complexity of disease management programs are highly heterogeneous. Some interventions did not improve patient outcomes, including an intensive model that involved close follow-up by their primary care provider, beginning before discharge and continuing for six months. These findings call for the need of additional models that could potentially account for both efficacy and efficiency, such as SMAs in HF. Our previous successes in SMAs for diabetes, and those of others, suggest that this approach to be an ideal setting to empower patients with HF self-care skills and induce change in self-care behaviors in HF in addition to medication management and disease monitoring to improve their symptoms and health status. However, effectiveness of SMAs in HF management is unknown, and unlike patients with diabetes, a mostly asymptomatic disease in its initial stages, HF patients are vulnerable, especially after hospitalization, with a constant risk of further decline in health status or death. Indeed the national VHA data showed that ~20% of these patients are readmitted within 30 days of their discharge.

As stated by a systematic review commissioned by the VHA QUERI on SMAs, there is little evidence on the effectiveness of SMAs in disease conditions other than diabetes and there are uncertain effects of SMAs on physiological variables other than HbA1c. A key gap noted in this recent meta-analysis of SMAs was the lack of evidence for SMAs in patients with HF. In our literature survey, there are only 3 small studies of SMAs in HF reported, and 1 RCT (n=198) that is single-center, in a non-VHA setting, education-focused (without disease monitoring or medication titration), and not targeted to the recently hospitalized population. Three small studies addressed different mechanisms at which HF-SMA may improve outcomes. An observational HF-SMA study (n=39) from the Naval Medical Center, San Diego, reported that HF-SMA resulted in improvements in self-care after 6 months. Another study (n=52) of HF-SMA found improvements in the HF knowledge in patients randomized to HF SMA. A pilot of 20 patients showed that satisfaction with SMA was high among patients and office staff. But, none of these studies reported significant differences in health status or hard endpoints. The single-center RCT showed trend toward improvement in hospitalization or death that support potential for HF-SMA in improving hard outcomes in this proposal. Because SMAs are not a pharmacotherapy, the precise elements of the intervention will differ by health condition and need to be elucidated and refined for HF, which will be effected in this proposal. Preliminary data from Providence VAMC and Phoenix VAMCs indicated that hospital readmission rates for HF patients enrolled in SMAs are lower than secular controls (details under pilot), but only 20-30% of patients are referred to HF-SMAs. A major barrier for increased local implementation is the lack of rigorous effectiveness data. Thus, there is a need for a rigorous assessment of effectiveness prior to being able to transfer the successes from diabetes SMAs to HF.

#### HF-SMA, Patient-Centered Care and Patient Aligned Care Teams (PACT)

HF-SMA is in alignment with the current VHA PACT principles, where access (currently a primary concern VHA wide) will be enhanced through SMAs (allows for up to 6 HF patients per session, with their caregivers if present), and patients will be exposed to a team of multi-disciplinary health care professionals, where they will receive more quantity of care but also quality of care due to providers of diverse expertise, in a single coordinated care program. Given that patients often have concerns that span several clinical disciplines (e.g. dietary, medications, lack of social support [who to call for problems], worsening health status), the opportunity of having a provider with needed expertise to help a given patient's problem is greater in this HF-SMA setting as opposed to the traditional one-provider clinic setting alone. Available evidence suggests that approaches targeting patient's needs for self-care and case management, such as the proposed HF-SMA, are likely the most clinically relevant and effective intervention for HF. This approach is also concordant with the Patient-Centered Medical Home model (which are also VHA PACT principles), characterized by: whole-person orientation, coordinated and integrated care, quality and safety and enhanced access. The Chronic Care Model (mapped in Figure 1 below) can help explain how the SMA approach can align the needs of the patients with existing hospital resources.

#### HF-SMA and Alignment of Health System Resources with Patient-Centered Care, the Chronic Care Model

[figure not shown]
The Chronic Care Model is a disease management approach comprised of 6 components: 1) care delivery system re-design (e.g. SMAs), 2) linking the patient to community resources (exposure to available community and VHA resources), 3) self-management support (e.g. education toward behavioral modification), 4) provider decision support, 5) use of electronic medical record system and 6) a system-wide commitment to quality. Both electronic medical record system and organizational commitment to quality are both VHA standards. Our proposed HF-SMA will build upon the pre-existing infrastructure to complete the components of the Chronic Care Model. The use of non-physician health care professionals in a group approach to

complement traditional physician care is another example of the system re-design. The medication reconciliation during HF-SMAs is a good example of provider decision support and preserves quality and safety of care by coordinating care from different multi-disciplinary providers, and should increase stakeholder (treating physician) satisfaction. The patient and care-giver education (self-management support) followed principles of patient-centeredness for patient empowerment and engagement and should enhance patient satisfaction. Additional HF-related care including disease monitoring, medication effect monitoring, and referrals into additional support programs (link to resources) addresses the patient-centered medical home principles of enhanced access, whole-person orientation, quality and safety, and integrated care.

#### Potential for HF-SMA to promote behavioral change

In addition to disease state monitoring and medication management, HF patients require intense training in self-care, such as weight monitoring and adherence to diet and medications, and early symptom recognition, which is difficult and time-consuming to provide in the traditional one-on-one visit setting. Based on the self-management support and system re-design constructs of the chronic care model, HF-SMA has the potential to address the self-care needs of these patients in a coordinated and efficient manner. The mechanisms at which the self-management support in HF-SMA could lead to behavioral modification can be explained, at least in part by the Social Cognitive Theory (Figure 1). Based on the Social Cognitive Theory, promotion of healthy self-care behaviors in the SMA setting such as sodium restriction, weight-monitoring and medication adherence can be explained by determinants at the personal and environmental levels. At the personal level, the SMA providers will use interactive discussions to shape expectations (anticipatory outcomes of a behavior) in an environment of peer support and use the group dynamic (environmental factor) to promote observational learning (behavioral acquisition that occurs by watching the actions and outcomes of other's behavior which include credible role models). The SMA provider will provide reinforcement for healthy behavior (both direct and vicarious); and will foster self-control (regulation of goal-directed behavior performance, self-monitoring, goal setting, problem solving and self-reward) through self-reinforcement and promotion of self-efficacy, to increase healthy behaviors stated above. In addition, social support is also increased through education of family and support members when present. Our previous studies of SMAs in diabetes have shown positive results in improvement in self-care behaviors and glycemic control.

**Figure 1. Theoretical Underpinning of HF-SMA Intervention**

#### Significance of HF-SMA:

Given the impact of HF to the US population and to the VHA, this proposal is significant because SMA is an innovative and potentially transformative care model to improve health status, and reduce hospitalization or death, for veterans with HF. The current proposal is also responsive to the VHA HSRD Research Priorities of "Assess innovative approaches to improve access...for a vulnerable veteran population," such as the one studied, with multiple comorbid illnesses. The challenge of providing patient-centered care for veterans with HF is an urgent problem due to an increasing limited access to health care providers, an increased HF prevalence due to an aging population and improved heart disease survival, and an acute care-focused health system. HF-SMA is a tool of system re-design that has the potential to provide patient-centered care in a resource-constrained system while enhancing patient access. Given the potential benefits and evidence of its efficacy in diabetes, use of SMA's have become a quality metric within the VA National Primary Care strategic plan, but steps of its use in HF is still unknown. Thus, this project will help determine whether SMAs should be deployed and how they can be used in HF care. The alignment of HF-SMA with PACT principles and the VA National Primary Care strategic plan will facilitate implementation if proven effective. Our qualitative assessment will also help VHA in the understanding of potential barriers to implement HF SMAs. Given the impact and the potential contributions to the VHA, we have the support from CHF QUERI ([name]), National Pact Coordinator ([name]) and the National Director for Cardiology ([name]) to help us disseminate our findings and design of wide implementation if proven effective (support letters attached).

## **B. INNOVATION**

The innovations are: 1) a rigorous and well-powered experiment to test the effectiveness of SMAs in HF is much needed to fill the knowledge gap on HF-SMA and its effects on outcomes meaningful to the patient, the provider and the VHA (aims 1-4). Given the 2-site design (East and West regions), we will be able to perform an assessment of *heterogeneity of treatment effects*, if any, and select out system factors (hospital/provider) if any, and patient subgroups that favored SMA intervention, even when the overall trial shows a non-significant result. 2) Our mixed method approach and the planned pre-implementation assessment will help understand potential mechanisms of benefit, if any, thereby, streamline and refine the intervention in the next iteration, in preparation for broader implementation. 3) Given the poor health status of patients with HF, traditional treatment settings required intensive physician involvement to show clinical efficacy, especially after hospitalization. Therefore, our study will address whether the addition of non-physician health professionals, via SMA approach, may improve patient outcomes. 4) If proven effective, our intervention will add another care delivery model to treat HF and possibly other complex chronic diseases alike that have frequent exacerbations. **The importance of developing a new and robust intervention to improve patient outcomes in HF cannot be overemphasized, especially given recent literature that showed not all interventions in HF work as planned.** Examples of such ineffective interventions are regular follow-up calls after discharge or close follow-up by primary care, which did not improve patient outcomes despite better patient satisfaction. Because experimental interventions can have a neutral or even negative effect on outcomes, we have chosen a neutral comparator (usual care) rather than an active comparator.

Thus, *this randomized-controlled trial to test the effectiveness of HF-SMA in improving patient outcomes after hospital discharge is timely and critically needed to create an innovative approach to HF management, and support patients with symptomatic HF. Currently, patients with HF may have limited options in traditional care models which strain system resources and fail to comprehensively address patient needs.*

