Aim 2: To compare between the intervention versus usual care arms in hospitalization or death at 90 and 180 days after the randomization. For this analysis Cox proportional hazards model will be utilized where the event is a composite outcome that represents either hospitalization or death. Any patient who does not experience the event by 180 days will be denoted as censored. The main exposure is treatment group and other covariates include patient demographic and comorbidity information as described above. We will examine the differences in outcome at both 90 and 180 days. The appropriateness of the proportional hazards assumption will be examined and any violation of the assumption will be addressed. The appropriateness of the functional forms of each covariate will be assessed through residual analysis.

Aim 3: To compare between the intervention versus usual care arms in the change from baseline in patient's (a) HF Self Care index and (b) BNP levels, we will use the same linear mixed-effects modeling approach as described in Aim 1.

Subgroup and Sensitivity Analyses: In order to understand potential heterogeneity of treatment effects, stratified analyses will be conducted by our randomization stratifiers such as co-interventions or not, ejection fraction ( $\geq 40\%$  &  $< 40\%$ ), and hospitalizations in the previous 6 months ( $> 2$  &  $\leq 2$ ). Given that baseline KCCQ scores, HF self-care behavior, comorbidity burden, depression symptoms and caregiver support could potentially change the outcome of HF, we will conduct test for multiplicative interaction between the condition of interest (e.g. depression with PHQ-8  $\geq 10$  vs.  $< 10$ ) and the study arm allocation (intervention vs. usual care arm) on the patient outcomes of interest described in Aims 1 and 2. *If any these interaction terms are significant at an alpha level of 0.05 or less*, subgroup analyses will be conducted (e.g. number of comorbidities below and above the median, baseline KCCQ scores above and below the median, and by presence or absence of significant depression symptoms or caregiver support) depending on the feasibility by sample size. Sensitivity analyses will be performed by study site to determine the impact of setting in our study findings and potential variation of findings.

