Sample Size and Power Considerations: The overall study sample will be 375 (225 patients from Phoenix VAMC and 150 patients from Providence VAMC). Statistical power for the aims 1 and 2 is estimated given these are the most relevant and the most restrictive in terms of power estimations. Under a conservative dropout rate of 15% for 180 days of follow-up for the main outcomes (Aims 1 and 2), we estimate the power with an effective sample size of 316 (15% less than the total sample) and a 2-sided significance level of 0.05 using nQUERY Advisor 7.0®. For aim 1, we assess the power to detect a clinically significant change in KCCQ of 5 points, assuming a baseline score of 63 (our preliminary studies), with a common standard deviation of 15 for the study arms, using a 2-sample t-test. For aim 2, we assess the power to detect a relevant decrease in rehospitalization or death risk of 25-30% at 180 days using a Cox Proportional Hazards model. Based on our preliminary data of 20,000 Veterans with ejection fraction <40% hospitalized with HF, their rehospitalization rates at 6 months is ~40%. Assuming similar event rates for rehospitalization or death, as shown in Table 2, we have good power to detect the proposed outcomes at very conservative estimates of effective sample size (n=158 in each arm, which is 85% of the total proposed recruitment target). Repeated measures at 90 and 180 days are also likely to add to the statistical power in Aim 1 to detect differences at the subgroup levels.

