**11. Limitations and potential shortfalls:** First, it is possible that secular trends such as an increase in the availability for co-interventions threaten our experimental design and cause underestimation of our treatment effects. We are using stratified randomization to balance current co-interventions and will track this carefully during the enrollment period. Adjusted analyses for imbalanced in exposure to co-interventions during follow-up will be performed when necessary and stratified analyses by co-interventions will also be explored as detailed in our analysis plan. In addition, it is likely that the effects of secular trends should be randomly distributed in a randomized controlled study, such that co-interventions should not have a differential effect. Second, our study duration is only 6 months. Based on our previous data on diabetes, the effect of SMAs on patient's outcomes are the highest while the patient is enrolled in the program and gradually declines after the stop of sessions unless booster sessions are planned. Given limitation of resources, we would like to test the short and mid-term effectiveness of the intervention first, prior to studying maintenance programs. Third, there is always a risk of not achieving the targets for patient recruitment. Fortunately, the project team is very experienced, and has had excellent track records in patient recruitment and retention in previous studies of similar characteristics. The use of 2 study sites will provide us with additional protection to achieve recruitment goals. Fourth, variation in effect size: It is possible that we found that the intervention may be effective in one site but not another, or in certain patient subgroups but the overall effect may not be large. This problem can arise due to distinct standards of usual care provided to patients and different settings of care. However, understanding these differences through this study will be important to know which settings and patients to target to derive the most benefits.

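### Stratifiers and site are compared with no interaction test, yet subgroup and site differences may guide whom to target even after a non-significant trial

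*Combined protocol and SAP*

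**What the plan says.** Four places in the combined protocol and SAP bear on this point.

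- **B. Innovation.** With two sites, the investigators expect to examine heterogeneity of treatment effect and to identify system factors and "patient subgroups that favored SMA intervention, even when the overall trial shows a non-significant result".
- **Item 9, Quantitative Analytic Plan, paragraph on subgroup and sensitivity analyses.** Two routes are given. In the first, "stratified analyses will be conducted by our randomization stratifiers such as co-interventions or not", together with ejection fraction and prior hospitalisations; site is handled by separate sensitivity analyses. Neither is preceded by an interaction test. In the second, five modifiers (baseline KCCQ, self-care, comorbidity, depression symptoms, caregiver support) are each tested for interaction with study arm on the outcomes of Aims 1 and 2. Subgroup analyses follow "If any these interaction terms are significant at an alpha level of 0.05 or less", as far as sample size allows.
- **Item 9, Sample Size and Power Considerations.** Repeated measures are said to be "likely to add to the statistical power in Aim 1 to detect differences at the subgroup levels". No subgroup power figure is given.
- **Item 11, Limitations and potential shortfalls.** If the effect appears at one site or in some subgroups but is not large overall, understanding the differences is said to show "which settings and patients to target to derive the most benefits".

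I found no multiplicity adjustment, no count of the interaction tests, and no statement that subgroup findings after a non-significant primary result are only hypothesis-generating.

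**The concern.** A claim that an intervention works in one group and not in another needs a direct estimate of the difference between the two effects. For the stratifiers and site, the plan produces only separate estimates within each stratum. One stratum can reach significance and the other miss it when the true effects are identical.

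For the five modifiers the right kind of test is used. However, it is repeated across modifiers and outcomes at 0.05, and the plan does not say how many tests will be run.

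This matters because of the stated use. The Innovation text looks for subgroups in one direction, towards the intervention, and expressly allows for a non-significant trial. The Limitations text gives the purpose, which is choosing patients and settings. What is at stake is how a non-significant trial would be interpreted. The primary comparison is not affected.

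**Working it through.** **1. The plan's own power figures.** Inputs from Sample Size and Power Considerations: 158 per arm, SD 15, two-sided 0.05. The standard error of the difference is 15 × √(2/158) = 1.688, and power is Φ(δ/1.688 − 1.96).

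| Difference | Computed | Table 2 |
|---|---|---|
| 4.5 | 0.760 | .76 |
| 5 | 0.842 | .84 |
| 5.5 | 0.903 | .90 |
| 6 | 0.945 | .95 |

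The Aim 1 column reproduces. The plan gives no corresponding figure for subgroups.

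**2. Chance of at least one false interaction among the five modifiers.** For k independent tests at 0.05 it is 1 − 0.95^k. The outcomes of Aims 1 and 2 are KCCQ, EQ-5D, and hospitalisation or death.

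- One outcome, 5 tests: 1 − 0.95^5 = 22.6%.
- Three outcomes, 15 tests: 1 − 0.95^15 = 53.7%.
- Three outcomes at both 90 and 180 days, 30 tests: 1 − 0.95^30 = 78.5%.

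The counts are inferred, because the plan does not fix them. A joint treatment-by-time-by-modifier test would need fewer.

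**3. Effect of correlation.** I simulated trials with no treatment effect: 316 patients and 4,000 runs per scenario. The following are assumptions, not figures from the documents: normal outcomes, modifiers split 50/50, modifier correlation 0 or 0.3, outcome correlation 0.3 or 0.6, and correlation 0.6 between 90 and 180 days. Five modifiers on three outcomes at two times gave 66–74%, against 78.5% under independence. The independence figures for several outcomes are therefore on the high side.

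**4. What separate strata can show.** Take a stratifier that splits the sample in half (an assumption), with 79 per arm in each half.

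- Suppose the true effect is 5 points in both halves, so there is no effect modification. The standard error in each half is 15 × √(2/79) = 2.387, and power is about 0.55. The chance that exactly one half is significant is 2 × 0.55 × 0.45 = 0.495.
- Suppose there is no effect in either half. The chance that at least one half is significant, in either direction, is 1 − 0.95² = 9.8% per factor.

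Discordant strata are thus expected about half the time when the two true effects are both exactly the plan's 5 points.

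**5. Illustration of power for an interaction.** For a 5-point difference between the effects in two equal halves, the standard error is 15 × √(4/79) = 3.375, so power is Φ(5/3.375 − 1.96) = 0.32. This uses SD 15, one time point and no baseline adjustment. Under other assumptions:

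- a 25/75 split: 0.25;
- averaging two visits correlated 0.6: 0.38;
- baseline adjustment at correlation 0.5–0.7, if 15 is the raw-score SD: 0.40–0.55.

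All are well below the 0.84 for the main comparison.

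**The case against.** The plan deserves credit on several counts. The five modifiers are named in advance, mostly with cited reasons. They must pass an interaction test before any subgroup is analysed, and feasibility by sample size limits what follows. A reader might infer that there is no error control at all; this gate shows otherwise, although it is itself unadjusted and the stratifiers and site do not pass through it.

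A reader might also infer that subgroups from a null trial feed the dissemination programme. The documents do not say so. Section E makes hospital-level and national implementation conditional on effectiveness, with the national step going through a further implementation trial. The Innovation text speaks of ability rather than a commitment, and the Limitations text concerns an overall effect that may not be large. What stands is that these two texts together describe choosing targets from subgroup and site differences, with no caveat.

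The plan does not say that strata will be compared by their p-values, and site is labelled a sensitivity analysis. That is fair. But without an interaction estimate, the planned output contains nothing that measures the difference.

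Finally, exploratory effect modification need not be adjusted for multiplicity. I accept this, provided the results are labelled exploratory and the number of tests is reported.

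**Conclusion.** The concern holds in this form: heterogeneity by stratifier and site is assessed by a method that does not test it, the five gated interaction tests are unadjusted and uncounted, and the stated use goes further than such results can support. The chance of a false interaction among the five modifiers is 22.6% for one outcome and at most about 53.7% for three, depending on the correlation between outcomes and on a test count that the plan leaves open.

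Three stronger conclusions are not supported.

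- **A false subgroup claim in favour of the intervention is likely.** In the same simulation, I added the stratifier and site strata (sites split 60/40) and counted any significant favourable stratum as a claim, with the gate applied to the five modifiers. The chance was 18–19% for KCCQ at 180 days and 28–32% for two outcomes at one time. It passed one half (52–59%) only for three outcomes at two times. The plan commits to none of these counts.
- **The stratifiers add to the number of interaction tests.** The plan runs no interaction test on them, so a larger count describes no procedure in it.
- **The sentence on repeated measures is wrong.** It claims only a direction and gives no figure. The 0.55 and 0.32 above illustrate that subgroup power is low; they do not correct a stated value.

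Parts of the protocol absent from the public text could contain a safeguard. That cannot be excluded.

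**What to change.** 1. **Item 9, subgroup and sensitivity analyses.** Assess the three stratifiers and site by treatment-by-factor interaction, as is already planned for the five modifiers. Separate prespecified models are acceptable. Report each interaction estimate with its 95% confidence interval, and give stratum and site estimates as descriptive only.
2. **Same paragraph.** List the full family of interaction tests, with KCCQ as the main outcome and the others exploratory, and report how many were done. A multiplicity adjustment is optional. For example, testing five modifiers on one outcome at 0.01 each gives 1 − 0.99^5 = 4.9%.
3. **B. Innovation and item 11, Limitations.** Reword both so that subgroup and site findings, above all after a non-significant primary result, are hypothesis-generating and are not used on their own to select target patients or settings.

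The cost is SAP wording and minor programming, with no change to design, visits or sample size. The downside is less scope to declare a subgroup benefit.
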